<Study Protocol>

**Prediction of pathologic complete response (pCR) by
preoperative biopsy in breast cancer with complete
clinical response (cCR) after neoadjuvant chemotherapy**

Version No: 3.0

(English version of Korean version approved by IRB on August 12, 2016)

Principal investigator:

[name], MD, PhD

Department of Surgery, Seoul National University Hospital

Department of Surgery, Seoul National University College of Medicine

Cancer Research Institute, Seoul National University

Study Overview

(※ Please provide a clear and concise description of each of the following sections in plain terms that can be understood by non-experts.)

Study Title	(Korean) 선행항암요법을 시행한 유방암 환자에서 유방자기공명영상 및 중심침생검 또는 맘모톰조직생검에 의한 병리학적 완전 관해 예측의 정확도에 대한 전향적 연구 (English) Prediction of pathologic complete response (pCR) by preoperative biopsy in breast cancer with complete clinical response (cCR) after neoadjuvant chemotherapy
Principal Investigator	[name] Department of Breast Endocrine Surgery, Seoul National University Hospital
Study Sponsor Institution	Seoul National University Hospital

Study Purpose	
 ● To develop a non-surgical and accurate method to determine the pathological complete response (pCR) in patients with breast cancer after neoadjuvant chemotherapy. ● To develop a basic examination technique that would allow screening of patients based on whether they need local resection or not, when making preoperative determination by pathological response.
Study Design	
 ● This is a prospective clinical trial. ● Patients with breast cancer, who underwent neoadjuvant chemotherapy and whose diagnostic imaging results, including breast magnetic resonance imaging (MRI), showed near complete or complete clinical response (i.e., no residual tumor) will be enrolled. ● On the day before the surgery or on the day of surgery, needle biopsy or vacuum-assisted biopsy will be performed in the eligible patients, focusing on the primary tumor and the peripheral area. The biopsied area will be localized with a wire. Wide excision will be performed subsequently. ● Accuracy of the prediction of pCR by breast MRI and multiple-core needle biopsy or vacuum-assisted breast biopsy will be determined by analysis of final pathological findings of the surgically removed breast tissue.
Study Period	August 12, 2016 ~ August 11, 2018

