Based on the above calculations, a total of 30 patients would be sufficient for this study. However, an additional 10 patients were included for further analysis to compare multiple-core needle biopsy and vacuum-assisted breast biopsy, thereby allowing 20 patients in each group.

Among the patients who were admitted for surgery after neoadjuvant chemotherapy (admitted 2 days before surgery), those who were expected to have a complete response immediately before surgery, based on the MRI and ultrasound results, will be given an explanation with regard to study plan, etc.

5. Study Method

1) Detailed study method

A. Breast MRI for assessing response after neoadjuvant chemotherapy

- Breast MRI diagnosis will be interpreted independently of clinical measurements, mammography, and breast ultrasonography results.
- Two breast MRIs will be done for patients who have received neoadjuvant chemotherapy, one before and one after the therapy.
- The images obtained before and after chemotherapy will be examined by a breast diagnostic imaging specialist to assess the exact response of the tumor to neoadjuvant chemotherapy and the presence of residual tumor.
- A complete MRI response means no abnormal contrast enhancement, no mass, or no distortion of the breast tissue in all phases of the MRI and in all compartments of the breast.
- A near complete MRI response means tumor size ≤ 0.5 cm or Lesion-to-Background Signal Enhancement Ratio [L-to-B SER] ≤ 1.6 .
- The response will be evaluated based on the results of breast ultrasonography and mammography, in addition to breast MRI. In case of residual tumor findings, such as clustered microcalcification on mammography, the patient will be excluded even when an abnormal contrast enhancement is not observed.

B. Biopsy in patients whose complete response is predicted by breast MRI

- In previous studies, attempts to predict the complete response using diagnostic images of breast alone showed about 21% false negative findings. Additional confirmation of pCR using multiple-core needle biopsy or vacuum-assisted breast biopsy can lower such false negative findings.
- A needle biopsy or vacuum-assisted breast biopsy will be performed around the residual tumor and the periphery and a wire will be inserted for localization of the biopsied area. The wire will guided the subsequent wide excision.

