- Multiple-core needle biopsy (14-gauge) or vacuum-assisted breast biopsy (10-gauge) will be performed. Obtaining at least five cores is recommended. Multiple-core needle biopsy will be performed at five different locations where the mass is seen before chemotherapy and in areas with the highest blood flow,

as seen in the color Doppler image or the lowest echo on B-mode ultrasound, thus indicating the highest likelihood of residual tumor. The clip inserted during the course of neoadjuvant chemotherapy will also be used as reference.

- To minimize variation while performing biopsy, two different radiologists, with at least five years of experience, will perform the biopsies at sites determined by consensus.
- Amongst the total 40 patients in this study, 20 will undergo multiple-core needle biopsy and 20 will undergo vacuum-assisted breast biopsy. The patients will be assigned alternatively. The prediction rates obtained from the two groups will be compared.
- The rate at which complete responses is achieved by neoadjuvant chemotherapy varies by breast subtype. According to the Seoul National University Hospital data, about 5% of hormone receptor-positive (HR+) breast cancers and 20% or more of Her2-positive (HER2+) or triple-negative breast cancers (TNBC) have shown complete response after neoadjuvant chemotherapy.
- When predicting complete response with breast MRI, PPV also showed high prediction rate for TNBC and non-hormone receptor expression/Her2 positive subtypes and about 45% prediction rate for luminal subtypes.

C. Determining factors that influence the accuracy of pCR prediction after neoadjuvant chemotherapy

- The accuracy of prediction of pCR by breast MRI is likely to be affected by subtypes of breast cancer and the size and location of the tumor prior to neoadjuvant chemotherapy. Thus, the clinical pathological factors that influence the accuracy of the prediction will be analyzed.
- Analysis will be performed by categorizing the tumors according to the patient's age, density of breast tissue (grade), and histological characteristics of the tumor.

2) Comparative group setting and randomization method

The patients will be alternatively assigned in a 1:1 ratio in the multiple-core needle biopsy group and vacuum-assisted breast biopsy group, such that one patient would receive multiple-core needle biopsy and the next will receive vacuum-assisted breast biopsy.

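### Strict alternation between core needle and vacuum-assisted biopsy leaves the next assignment foreseeable; a concealed shuffled list would be a cheap, minor improvement

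*Combined protocol and SAP*

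**What the plan says.** Section 5.2) assigns patients 1:1 so that "one patient would receive multiple-core needle biopsy and the next will receive vacuum-assisted breast biopsy". Section 5.1)B says the same: "The patients will be assigned alternatively". The heading of 5.2) refers to randomization, but the text beneath it describes alternation only. No list, list holder, envelope or central assignment appears anywhere in the document. The randomised design mentioned in Section 2.2)B concerns surgery versus no surgery, not the two biopsy methods.

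The comparison is planned in the Study Overview (Study Method) and in Sections 4.4), 5.1)B and 5.9). Section 4.4) says that "an additional 10 patients were included for further analysis to compare multiple-core needle biopsy and vacuum-assisted breast biopsy". Section 5.9) places it after the endpoint list as an additional analysis and does not fix its measure.

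On recruitment, Section 4.4) has the team approach patients admitted two days before surgery, specifically "those who were expected to have a complete response immediately before surgery, based on the MRI and ultrasound results". Section 4.1) says all patients who meet the MRI criterion are to be included (tumour size ≤ 0.5 cm or L-to-B SER ≤ 1.6).

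**The concern.** Whoever decides whether to approach a patient can know both that patient's imaging findings (and presumably the tumour subtype) and which biopsy method comes next. Concealment exists to separate those two pieces of knowledge. Without it, the groups could come to differ in case mix for reasons other than chance, and a confidence interval does not allow for that.

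Case mix matters because the probability of pCR differs by subtype. Section 5.1)B reports that on MRI "PPV also showed high prediction rate for TNBC and non-hormone receptor expression/Her2 positive subtypes and about 45% prediction rate for luminal subtypes". Section 5.1)C adds that "The accuracy of prediction of pCR by breast MRI is likely to be affected by subtypes of breast cancer"; that sentence is about prediction by MRI and does not say that biopsy accuracy varies by subtype. NPV, the primary endpoint named in 5.9), changes with pCR prevalence even when two biopsy methods perform identically. If NPV is the measure compared, a difference in subtype mix would look like a difference between methods.

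**Working it through.** **The plan's own figures.** Section 4.3) gives p0 = 0.64, p1 = 0.90, one-sided α = 0.05 and power 80%.

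- n = (1.645 × √(0.64 × 0.36) + 0.842 × √(0.90 × 0.10))² / 0.26² = 1.0420² / 0.0676 = 16.06, rounded up to 17.
- 17/0.64 = 26.6, so 27; 27/0.9 = 30; 30 + 10 = 40.

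All match the protocol, and none depends on how the groups are formed.

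**Foreseeability.** Under alternation, 39 of 40 assignments are certain once the first is seen, and all 40 if the starting method is fixed. For one shuffled 20:20 list, someone who sees every past assignment and guesses optimally is right on average 20 + (4²⁰/C(40,20) − 1)/2 = 20 + (7.98 − 1)/2 = 23.5 times in 40 (59%). Only about 1.9 assignments are then certain.

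**Possible bias when the methods are identical.** Inputs:

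- specificity 0.90 and pCR 64% (Section 4.3);
- pCR 45% in luminal patients (the Section 5.1)B figure, read as the share of MRI-predicted responders who have pCR);
- sensitivity for residual tumour 0.70 to 0.90 (assumed; not in the documents);
- pCR in non-luminal patients 75% to 90% (assumed).

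NPV = 0.90p / [0.90p + (1 − sens)(1 − p)], where p is the pCR prevalence. At p = 0.64, NPV is 0.842 (sens 0.70) or 0.941 (sens 0.90).

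Suppose three luminal patients are not approached when one particular method is next, and each is replaced by a patient with pCR probability r. That group of 20 then has p = 0.64 + 3(r − 0.45)/20.

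| Replacement | r | p | NPV gap, sens 0.70 | NPV gap, sens 0.90 | Pooled NPV shift, sens 0.70 / 0.90 |
|---|---|---|---|---|---|
| Average patient | 0.64 | 0.6685 | 1.6 points | 0.7 points | 0.8 / 0.3 points |
| Non-luminal, low | 0.75 | 0.685 | 2.5 points | 1.0 points | 1.3 / 0.5 points |
| Non-luminal, high | 0.90 | 0.7075 | 3.7 points | 1.5 points | 1.9 / 0.8 points |

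A larger shift, to pCR of 69% v 59%, gives a gap of 0.870 − 0.812 = 5.8 points (sens 0.70) or 0.952 − 0.928 = 2.4 points (sens 0.90). Solving 0.45x + h(1 − x) = p for the luminal share x, this needs 4.0 v 10.7 luminal patients per 20 (h = 0.75) or 9.3 v 13.8 (h = 0.90). A table of subtype by group would show that.

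The accuracy gap at 69% v 59% is (0.90 − sens) × 0.10, or 0 to 2 points. The false negative rate does not move, provided biopsy sensitivity is the same in every subtype.

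**Precision.** Expected biopsy-negatives per 20 are 20 × [0.90 × 0.64 + (1 − sens) × 0.36] = 13.7 (sens 0.70) or 12.2 (sens 0.90). The 95% half-width for the NPV difference is 1.96 × √(2 × NPV × (1 − NPV)/negatives) = 27.3 or 18.6 points. For accuracy (0.828 or 0.900), 1.96 × √(2a(1 − a)/20) = 23.4 or 18.6 points.

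**Opportunity to swap the order of two patients.** The study period is "August 12, 2016 ~ August 11, 2018", 730 days for 40 patients. If arrivals are even and random over that time, the chance of another enrolled patient within two days either side is 1 − exp(−4 × 40/730) = 20%. Selective enrolment would mostly mean not approaching someone.

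**The case against.** The strongest case against is that this hardly matters here. As written, Section 4.1) leaves no discretion to pass over an eligible patient, and its thresholds are numeric. The Study Overview and Section 5.1)C plan to examine factors that influence prediction, including subtype. Both biopsies are established procedures and every patient goes on to excision, so no motive for steering is apparent. The comparison is peripheral: with 20 v 20, power is about 50% even for 0.90 v 0.64 (two-sided 0.05, normal approximation). With a bias of 0.7 to 3.7 points, a nominal 95% interval for the NPV difference would still cover about 94.2% to 95.0% of the time. The heading may also simply come from a form, since other inapplicable sections are kept and marked as such.

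Most of this stands, and it sets the severity. It does not remove the point. None of these safeguards hides the next assignment, no screening log or consecutive-enrolment rule is stated, and the factor analysis is not an adjusted comparison of methods.

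A reader might go further and infer that the plan has no protection at all against selective enrolment, that patients were steered, or that the protocol passes off a non-randomised trial as randomised. The documents support none of these. The partial safeguards are real, foreseeability is a risk in the design and not evidence of conduct, and the text under the heading describes alternation openly.

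**Conclusion.** The point holds as a minor weakness: assignment is foreseeable and unconcealed for a planned comparison that accounts for a quarter of the patients (10 of 40). The bias range applies if NPV is compared, about three luminal patients are passed over for one group, specificity is 0.90 and overall pCR 64%, and the assumed sensitivity and non-luminal pCR ranges hold. It is well inside the sampling error.

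It would be tempting to conclude that the primary result is compromised. That does not follow. The pooled NPV has no comparison group and does not depend directly on allocation. Only if patients went unapproached could its case mix move, by 0.3 to 1.9 points in the cases above.

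**What to change.** In Section 5.2), replace alternation with one computer-generated, fully shuffled 20:20 list. Existing staff not involved in enrolment should hold it, or it should be placed in sequentially numbered sealed opaque envelopes. Each assignment should be opened only after eligibility and consent are recorded. A single shuffle is preferable to small fixed blocks: with blocks of four, the best guess is right about 71% of the time and about 13 of 40 assignments are certain.

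The cost is minor logistics, a wording amendment, and slightly unequal groups if accrual stops before 40. The total stays at 40 and neither biopsy procedure changes. The list will not make the comparison precise or prevent chance imbalance: the SD of the between-group pCR difference is √(2 × 0.64 × 0.36/20), about 15 points. The confidence interval does allow for that chance variation.

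If alternation is kept, remove the reference to randomization from the heading, label the comparison exploratory and non-randomised, and tabulate subtype by group. That costs only wording and one table.
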